1.1 Background and Rationale

Alzheimer's disease (AD) is a progressive neurodegenerative disorder characterized by synaptic dysfunction, neuronal loss, and accumulation of pathological protein aggregates. Current standard treatments, including acetylcholinesterase inhibitors (AChEIs) such as donepezil, provide modest symptomatic benefit but do not address underlying disease mechanisms or halt neurodegeneration.

Phenserine is a next-generation AChEI with additional non-cholinergic mechanisms that may confer disease-modifying properties. Preclinical and clinical evidence indicates that phenserine modulates pathways related to pre-programmed cell death, synaptic integrity, neuroinflammation, and amyloid precursor protein processing. Unlike currently approved AChEIs, phenserine has demonstrated effects on molecular markers associated with neuronal survival and apoptosis, including Bcl-2, caspase signaling, and neurotrophic factors.

Previous clinical development programs of phenserine were conducted primarily in patients with mild-to-moderate AD and were limited by suboptimal dosing strategies, lack of biomarker confirmation of AD pathology, and insufficient characterization of pharmacodynamic effects. These limitations support the need for a refined early-phase study focused on mechanistic biomarkers and individualized dose optimization.

The full rationale for undertaking the trial and trial background is explained in detail in the protocol. This Statistical Analysis Plan (SAP) describes the statistical methodology and data handling procedures for the PATH-1 study, a Phase 1b randomized, open-label, parallel-group trial comparing phenserine with donepezil in participants with early or mild Alzheimer's disease (AD).

The SAP is finalized prior to database lock and unblinding of biomarker results and is written in accordance with ICH E9 and relevant EMA guidance for early-phase exploratory trials. Any deviations from this SAP will be documented in a separate SAP amendment prior to database lock.

2 Study Objectives and Endpoints

2.1 Primary Objective

To assess the effects of phenserine compared to donepezil on exosome biomarkers of pre-programmed cell death, synaptic integrity, neuroinflammation, and AD-related protein trafficking.

2.2 Secondary Objectives

- To evaluate safety and tolerability of phenserine versus donepezil
- To characterize PK–PD relationships
- To assess achievement and maintenance of ~45% AChE inhibition
- To assess treatment compliance

2.3 Exploratory Objectives

- Changes in CSF and plasma AD biomarkers
- Short-term cognitive effects using FLAME and MoCA

Endpoints are defined exactly as per Protocol Section 3 and Table 2

2.3.1 Hypothesis Framework

This trial is an exploratory Phase 1b dose range–finding study designed to characterize the pharmacodynamic, pharmacokinetic, and safety profile of phenserine compared with donepezil in participants with early or mild Alzheimer's disease. The study is not powered for formal confirmatory hypothesis testing.

The primary objective is mechanistic and descriptive in nature, focusing on changes in exosome-derived biomarkers associated with pre-programmed cell death, synaptic integrity, neuroinflammation, and AD-related protein trafficking.

Primary Hypothesis Framework

- Null hypothesis (H_0): There is no difference between phenserine and donepezil in changes from baseline in exosome biomarkers over the 8-week treatment period.
- Alternative hypothesis (H_1): Treatment with phenserine is associated with changes from baseline in exosome biomarkers that differ from those observed with donepezil over the 8-week treatment period.

These hypotheses will be **exploratorily** evaluated through estimation of treatment effects and their associated uncertainty (95% confidence intervals), rather than formal hypothesis testing with a pre-specified significance level. The focus is on estimating the magnitude and direction of treatment differences.

Secondary and Exploratory Analyses

There is a single identified primary analysis related to exosome biomarker changes. All secondary (safety, PK, AChE inhibition, compliance) and exploratory (CSF, plasma biomarkers, cognitive outcomes) analyses will be considered supportive or exploratory and will be interpreted descriptively.

No formal non-inferiority or superiority margins are prespecified, and no multiplicity adjustments will be applied.

2.3.2 Confidence Intervals and p-values

P-values will be reported for descriptive purposes only and will be interpreted cautiously in the context of the exploratory study design. All efficacy estimates will be presented with two-sided 95% confidence intervals, which should be interpreted as ranges of plausible treatment effects rather than formal inference tools. As there is only one primary null hypothesis to be tested in this trial, there will be no adjustments for multiplicity.

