2.3.4. Overall Benefit Risk Conclusion

Overall, there is strong pre-clinical evidence of phenserine's biological effects that are relevant to the treatment of AD and other neurodegenerative conditions, with a novel effect on apoptosis in addition to cholinesterase inhibition. Previous clinical trials with phenserine suggest a good clinical safety profile and offer some encouraging indications of potential benefit. The protocol has been designed based on the learnings of the failed Axonyx program and will ensure that the patient population is appropriate and that the study assessments more fully characterize phenserine's potential therapeutic utility across more robust measures of pharmacodynamic effects and any correlated improvements in cognitive function.

3. Objectives, and Endpoints

The study will be conducted as a 2 arm, parallel group, randomized RCT of phenserine compared to donepezil in people with early or mild AD. A total of 16 participants will be recruited from sites across Norway and be supported by the PROTECT platform. Eligible participants will be randomized 6:2 to phenserine or donepezil in an unblinded manner.

The end of the research active period for this study is set to January 1, 2028. All analyses within the scope of this study will be completed by this date.

The pharmacodynamic (PD), pharmacokinetic (PK), and safety data from this study are intended to inform dose selection and study design for a subsequent Phase 2 study of phenserine over a longer treatment duration in people with early to mild Alzheimer's disease (AD). The objectives of the study are as follows:

Primary Objective:

To assess the effects of phenserine compared to donepezil on exosome biomarkers of cell death in people with early or mild AD.

Key Secondary Objective:

To evaluate the safety and tolerability profile, of phenserine at ascending doses up to 10 mg tds as compared to donepezil at doses up to 10 mg od in participants with early or mild AD.

Other Secondary Objectives:

To evaluate steady state blood levels of phenserine for the purpose of characterizing and comparing dose-response relationships for pharmacodynamic outcomes and key safety assessments.

To evaluate the proportion of participants in the phenserine arm who achieve the target AChE inhibition of approximately 45%, stratified by dose regimen and the time required to reach the target AChE inhibition of ~45% and the duration participants maintain this inhibition during the treatment period.

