3.2. Outcome Measures

3.2.1. Primary Outcome Measure

The primary outcome measure will assess changes in four panels of exosome biomarkers, including markers of pre-programmed cell death, synaptic integrity and function, neuroinflammation, and AD-related protein trafficking in participants treated with phenserine versus those treated with donepezil. Panel details are presented in separate standardized operationalized procedures (SOPs).

Although participants and site staff will be unblinded to the treatment modality administered, they will be blinded to the results of the exosome and blood/CSF biomarker evaluations until the study is completed.

The pre-programmed cell death panel (PNCDD) will investigate key factors such as BAX, Bcl-2, which will provide insights into preprogrammed cell death processes (4,17) and any changes in the profile observed following treatment with phenserine or donepezil. The second panel focuses on synaptic markers, including synaptotagmin, offering a nuanced understanding of synaptic integrity and function. The third panel is centered on evaluating inflammatory biomarkers, including TNF- α , IL-1 β , IL-6, and IL10, and the fourth panel will evaluate AD-specific markers, including A β 1-42, and will elucidate key molecular signatures associated with AD pathology. This comprehensive evaluation of mechanistic biomarkers through exosome technologies aims to deliver a detailed understanding of the impact of phenserine versus donepezil on various facets of AD neuropathology, contributing to the trial's primary objective.

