10.3.1. General Considerations

The statistical analysis plan for this study is designed to assess the efficacy, safety, and pharmacokinetic properties of phenserine compared to donepezil in participants with early or mild Alzheimer's Disease (AD). Analyses will be conducted on a modified intent-to-treat (mITT) population, which includes all randomized participants who receive at least one dose of study medication and have at least one post-baseline assessment. All statistical tests will be two-sided, with a significance level set at 0.05.

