4.5 Overview of Outcomes

An overview of the primary, secondary, and exploratory outcomes included in the PATH-1 study is provided in Table 4.4-1. Outcomes are categorized by level, timeframe, and data type to clarify their role in the statistical analyses.

Overview of Study Outcomes

Level	Outcome	Timeframe	Outcome Type
Primary	Change from baseline in exosome biomarkers of pre-programmed cell death, synaptic integrity, neuroinflammation, and AD-related protein trafficking	Baseline to Week 8	Continuous
Secondary (Key)	Safety and tolerability (AEs, SAEs, labs, ECGs, vital signs)	Throughout study	Categorical / Continuous
Secondary	Steady-state pharmacokinetic parameters (e.g. plasma concentrations)	Weeks 2–8	Continuous
	Proportion achieving target AChE inhibition (~45%)	During treatment	Dichotomous
	Time to achievement of target AChE inhibition	During treatment	Time-to-event
	Duration of maintenance of target AChE inhibition	During treatment	Continuous

	Treatment compliance (capsule count, diary)	During treatment	Continuous / Categorical
Exploratory	Change in CSF biomarkers (A β 1-40, A β 1-42, Tau, p-tau)	Baseline to Week 8	Continuous
	Change in plasma biomarkers (p-tau217, NfL)	Baseline to Week 8	Continuous
	Change in FLAME cognitive domain scores	Baseline to Week 8	Continuous
	Change in MoCA total score	Baseline to Week 8	Continuous

5 General Statistical Principles

- All analyses will be conducted using R (version ≥ 4.2) or SAS (version ≥ 9.4)
- Continuous variables: mean, SD, median, IQR, min, max
- Categorical variables: counts and percentages
- No formal hypothesis testing or multiplicity correction
- Emphasis on effect size estimation, confidence intervals, and visualizations
- Outliers and extreme values in biomarker measurements will be retained in primary analyses unless determined to result from assay or data collection errors. Sensitivity analyses may exclude extreme values (e.g., >10 MAD from median) to assess their influence on results. If performed, such analyses will be justified and documented.
- No formal subgroup analyses are pre-planned. Exploratory descriptive summaries may examine biomarker responses by baseline disease severity (early vs. mild AD) or by achievement of target AChE inhibition, but these will be clearly labeled as descriptive and post-hoc.

6 Handling of Missing Data

- No imputation will be performed for missing biomarker or cognitive data
- Analyses will use observed data only in a complete-case manner

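### SAP 2.3.2 waives multiplicity adjustment because there is one primary null hypothesis, but the primary endpoint covers four panels and at least eight markers at four visits, with no lead marker or contrast named

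*SAP*

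**What the plan says.** **SAP.** Section 2.3.1 says: "There is a single identified primary analysis related to exosome biomarker changes". It states one null hypothesis, covering exosome biomarkers in general over the whole treatment period, and says it will be judged by estimates and intervals without a preset significance level. Section 2.3.2 then gives the reason for making no adjustment: "As there is only one primary null hypothesis to be tested in this trial, there will be no adjustments for multiplicity". The same section says "P-values will be reported for descriptive purposes only and will be interpreted cautiously in the context of the exploratory study design" and "All efficacy estimates will be presented with two-sided 95% confidence intervals". Section 5 adds: "No formal hypothesis testing or multiplicity correction".

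**Protocol.** Section 3.2.1 says: "The primary outcome measure will assess changes in four panels of exosome biomarkers". The markers it names are BAX and Bcl-2 (cell death), synaptotagmin (synaptic), TNF-alpha, IL-1beta, IL-6 and IL-10 (inflammation) and A-beta 1-42 (AD-specific). Each list is open-ended and the panel details are left to SOPs. Section 10.3.1 says: "All statistical tests will be two-sided, with a significance level set at 0.05". Section 10.3 claims 80% power at that level for one between-group comparison.

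**Analysis.** Protocol 10.3 describes a mixed model for a given biomarker. SAP 7.2 gives a model with treatment, four categorical visits and their interaction, and separately lists mean change differences with 95% intervals. The outcome table in SAP 4.5 gives the primary time frame as baseline to Week 8.

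**Objective.** The primary objective in Protocol section 3 is narrower than the endpoint: "To assess the effects of phenserine compared to donepezil on exosome biomarkers of cell death in people with early or mild AD". SAP 2.1 widens the objective to all four domains.

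**The concern.** The single null hypothesis is an umbrella sentence with no test statistic attached. Beneath it are at least eight marker-level comparisons at each of four visits, and none is singled out. The premise of the waiver is therefore not met.

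The SAP also contradicts itself and the protocol. It refers to a hypothesis to be tested but plans no formal testing, while the protocol sets a 0.05 level and powers a comparison at it.

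The practical risk lies in reporting. Unadjusted p-values and 95% intervals will be produced, and whichever marker and visit look best could be presented as the primary finding. Protocol 2.3.3 says the results will be used to choose doses and outcome measures for Phase 2, so a chance marker could be carried forward as an outcome.

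**Working it through.** **Inputs.** Two-sided 0.05 (Protocol 10.3.1), 95% intervals (SAP 2.3.2), 12 phenserine and 4 donepezil (SAP section 3), and a difference of 2.45 SD with 4 per arm for 80% power (Protocol 10.3). The sample-size figure in Protocol 10.4 is garbled, so 10.3 is used. Markers named: 2 + 1 + 4 + 1 = 8, a minimum because the lists are open. Visits: 4. Contrasts: 8 × 4 = 32.

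**The plan's own figure.** For a two-sided t-test with 4 per arm, the noncentrality is 2.45/√(1/4 + 1/4) = 3.46 on 6 degrees of freedom, and power is 82.1%. With 3 per arm it is 61.9%. Four per arm is reproduced, but for one comparison at 0.05.

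**Chance of at least one nominal finding, no effect, independent tests.** The formula is 1 − 0.95^k, with 0.05k false positives expected.
- k = 4 (one score per panel): 18.5%, 0.2 expected
- k = 8 (named markers, one visit): 33.7%, 0.4 expected
- k = 32 (named markers, four visits): 80.6%, 1.6 expected

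**Allowing for correlation.** The documents give no correlations, so a range was simulated: 12 versus 4, pooled t-test, exchangeable correlations, 20,000 null trials per setting.

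| Marker correlation | Any of 32, visit correlation 0 | 0.5 | 0.8 | Any of 8 at Week 8 |
|---|---|---|---|---|
| 0 | 81% | 75% | 64% | 34% |
| 0.3 | 77% | 70% | 59% | 30% |
| 0.5 | 70% | 63% | 52% | 26% |
| 0.8 | 52% | 45% | 34% | 16–17% |

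The visit columns 0.5 and 0.8 are the relevant ones. Changes at different visits share the same baseline value. With independent errors of equal variance σ², each change has variance 2σ² and any two have covariance σ², which gives a correlation of 0.5. The range for 32 contrasts is then 34 to 75%. The expected number of false positives stays at 32 × 0.05 = 1.6 whatever the correlation.

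**What adjustment would cost.** With 12 versus 4 the noncentrality at 2.45 SD is 2.45/√(1/12 + 1/4) = 4.24 on 14 degrees of freedom.

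| Bonferroni family | Level | Power at 2.45 SD | Difference detectable with 80% power |
|---|---|---|---|
| 1 | 0.05 | 97.6% | 1.74 SD |
| 8 | 0.00625 | 82.4% | 2.39 SD |
| 32 | 0.0015625 | 62.9% | 2.82 SD |

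These use a single-visit t-test, not the mixed model. On the plan's own effect assumption, adjusting across eight Week 8 markers still leaves about 80% power.

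**The case against.** The strongest defence is that non-adjustment does not depend on the faulty sentence. SAP 2.3.1, 2.3.2, section 3 and section 5 all describe an exploratory, estimation-based study with descriptive p-values. Delete the sentence and the analysis is unchanged. That stands. A reader might infer that a confirmatory error rate has been lost, but the SAP claims none, and a 16-person Phase 1b trial need not have one.

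A reader might also infer that a chance finding is likely. That holds for 32 contrasts unless the correlations are high. If the SAP 4.5 time frame is taken to fix Week 8, the chance is 16 to 34%. The null hypothesis in SAP 2.3.1 refers to the whole eight weeks, so the documents leave this open.

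Four further inferences go too far:
- SAP 7.2 promises intervals and an exploratory model. It does not promise a p-value for each of the 32 contrasts.
- The documents say the data inform Phase 2 dose, outcome measures and design. They contain no go/no-go rule.
- Having only four comparators does not raise the false-positive rate of a valid t-test.
- The narrower cell-death objective is the protocol's. SAP 2.1, the protocol endpoint and its primary hypothesis cover all four domains.

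The defence does not reach two faults. The stated reason is incorrect and conflicts with the protocol's 0.05 level and power claim. And even a purely descriptive plan needs one identified primary estimate.

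**Conclusion.** The waiver sentence is wrong as written, and the plan names no primary contrast. With no effect, the chance of at least one nominal p<0.05 is about 16 to 34% for eight markers at Week 8 and about 34 to 75% for 32 marker-by-visit contrasts, against the 5% that a single hypothesis would imply. These ranges assume marker correlation of 0 to 0.8, visit correlation of 0.5 to 0.8, and exactly eight markers. The SOP list may be longer, which would raise them.

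The consequence is selective reporting of a primary result, not loss of a confirmatory error rate. The change should be made, but the point does not invalidate the design.

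**What to change.** Before database lock and biomarker unblinding:

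1. Delete the quoted sentence from SAP 2.3.2 and rest non-adjustment on the exploratory framing. Reconcile this with Protocol 10.3.1 and the power statement in Protocol 10.3 and 10.4, so that the documents agree on whether anything is tested at 0.05.
2. Name one primary contrast: phenserine minus donepezil at Week 8 from the mixed model, for a single marker or score from the pre-programmed cell-death panel. This matches the protocol's primary objective. Define the marker or score from the SOP panel list.
3. List every marker in the SAP and report all of them. For the Week 8 markers, show Holm- or FDR-adjusted p-values beside the unadjusted ones. Treat Weeks 2 to 6 as descriptive.

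The cost is mainly SAP wording, plus aligning the protocol text. The lead marker or score must be fixed now, and the adjusted p-values will be less favourable. The other three panels can stay in the primary outcome as reported results. Formally demoting them would be a protocol-level endpoint change, which this point does not require.

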2.4 Timing of Outcome Assessments

The timing of all outcome assessments is predefined in the study protocol and summarized in the Schedule of Activities (SoA) (Protocol Section 1.3, Table 1). Outcome measures are collected at screening, baseline, and at scheduled on-treatment and follow-up visits during the 8-week treatment period and safety follow-up.

For all clinically planned outcome measures, visits should occur within the predefined visit windows. Assessments performed outside the allowable visit window will be considered protocol deviations, unless otherwise justified and documented. Only assessments obtained within the protocol-specified windows will be used for primary and secondary analyses.

The target days and visit windows relevant for efficacy, pharmacodynamic, pharmacokinetic, and safety analyses are defined as follows:

Visit Label	Visit Window
Screening	Within 28 days prior to baseline
V1: Baseline / Randomization	Day 0
V2: Week 2	Day 14 ± 3 days
V3: Week 4	Day 28 ± 3 days
V4: Week 6	Day 42 ± 3 days
V5: Week 8 / End of Treatment	Day 56 ± 3 days
Safety Follow-up / EOS	Within 28 days after last dose

Assessments collected outside the visit window will not be included in the primary analysis but may be listed and summarized descriptively.

3 Study Design Overview

- Design: Open-label, randomized (6:2), parallel-group Phase 1b study
- Treatment Arms:
 - Phenserine (dose-escalation up to 10 mg TDS)
 - Donepezil (5–10 mg OD)
- Treatment Duration: 8 weeks
- Sample Size: n = 16 (Phen: n=12; Donepezil: n=4)

Given the exploratory nature and small sample size, all analyses will be descriptive, and estimation focused.

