3.3 Withdrawal and Follow-up

Participant disposition and withdrawal status will be summarized by treatment group. Levels of withdrawal will be categorized as follows:

- Completed study intervention and all scheduled assessments
- Completed scheduled assessments but did not complete study intervention
- Withdrew from study intervention but continued follow-up
- Withdrew consent for further participation
- Lost to follow-up

The number and percentage of participants in each category will be tabulated by treatment arm and overall. Reasons for withdrawal or loss to follow-up will be summarized descriptively.

Participants who discontinue study treatment but provide post-baseline outcome data will be included in the relevant analysis populations according to the definitions specified in Section 4. Early termination visits will be mapped to the end-of-treatment time point where applicable.

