3.4.2 Protocol Deviations

A protocol deviation is defined as any departure from the approved protocol, including but not limited to deviations related to eligibility criteria, study treatment administration, study assessments, or visit scheduling.

Protocol deviations will be prospectively classified as major or minor prior to database lock and prior to unblinding of biomarker results.

Major Protocol Deviations

Major protocol deviations are defined as deviations that may affect participant safety, the scientific integrity of the study, or the interpretability of the primary endpoint.

Predefined major protocol deviations include:

- Failure to meet inclusion or exclusion criteria with enrolment into the study
- Receipt of incorrect study treatment or dose not consistent with protocol-defined escalation rules
- Discontinuation of study treatment prior to completion of the dose-escalation phase without post-baseline biomarker data
- Use of prohibited concomitant medication with potential impact on safety or pharmacodynamic outcomes
- Missing all post-baseline exosome biomarker assessments

Participants with major protocol deviations may be excluded from specific analysis populations as defined in Section 4.

Minor Protocol Deviations

Minor protocol deviations include deviations that are not expected to materially affect safety or interpretation of study outcomes, such as:

- Study visits conducted outside the protocol-defined visit window
- Isolated missed or delayed assessments
- Administrative or documentation errors

Summary of Protocol Deviations

Protocol deviations will be summarized descriptively by treatment group and overall. The following summaries will be provided:

- Number and percentage of participants with at least one protocol deviation
- Number and percentage of participants with at least one major protocol deviation
- Number and percentage of participants with at least one minor protocol deviation

- Listing of protocol deviations by category and type

Percentages will be calculated using the randomized population as the denominator. No formal statistical testing will be undertaken.

4 Analysis Populations

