7.2 Statistical Methods

- Change from baseline will be calculated for each time point
- Within-arm trajectories will be visualized using spaghetti plots
- Between-arm comparisons will use:
 - Mean change differences with 95% CI
 - Mixed-effects models will be fitted exploratorily to estimate treatment effects over time.
 - Model specification:
 - Response: Change from baseline in biomarker level;
 - Fixed effects: Treatment (phenserine vs donepezil), Visit (categorical: Weeks 2, 4, 6, 8), Treatment × Visit interaction.
 - Random effects: Random intercept per participant.
 - Covariance structure: Unstructured (if convergence permits, otherwise compound symmetry).
 - Given the small sample size, models may have convergence issues or unstable variance estimates. If models fail to converge, results will be presented descriptively.

8 Secondary Analyses

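### SAP 2.4 drops exosome samples taken more than 3 days off target from the primary analysis, though SAP 3.4.2 calls such visits minor; each donepezil loss costs 1 of 4 comparator values at that visit.

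*SAP*

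**What the plan says.** SAP 2.4 sets windows of 3 days either side of Days 14, 28, 42 and 56 and states the exclusion twice. The first statement covers primary and secondary analyses: "Only assessments obtained within the protocol-specified windows will be used for primary and secondary analyses". The second is specific to the primary analysis: "Assessments collected outside the visit window will not be included in the primary analysis but may be listed and summarized descriptively". The proviso in the same section about justified and documented departures decides only whether a visit counts as a deviation. It does not bring the data back.

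SAP 3.4.2 gives "Study visits conducted outside the protocol-defined visit window" as an example of a minor deviation, and describes minor deviations as "deviations that are not expected to materially affect safety or interpretation of study outcomes".

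SAP 3.3 adds: "Early termination visits will be mapped to the end-of-treatment time point where applicable". It sets no day limit and does not say whether this overrides the window rule.

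Three other provisions matter:
- SAP 3 gives 12 phenserine and 4 donepezil participants.
- SAP 6 specifies observed data, no imputation and a complete-case approach.
- SAP 7.2 plans simple differences in mean change, plus a mixed model with treatment, categorical visit, their interaction and a random intercept.

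The protocol's analysis text (10.3) contains no window exclusion.

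**The concern.** The SAP judges a late or early visit harmless to interpretation and then leaves its biomarker value out of the primary comparison. No reason is given. SAP 5 is more lenient with extreme biomarker values, which stay in the primary analysis unless they come from assay or data collection errors.

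The comparator has only four people, and SAP 2.3.1 says the output is an estimate with a 95% confidence interval. What is at stake is therefore the width of that interval, above all at Week 8. The sample size text makes no allowance for lost samples, and Protocol 10.1 replaces only participants who leave before taking drug or before the first assessment.

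**Working it through.** **Plan's own figure.** Protocol 10.3 says 4 per arm gives 80% power for 2.45 SD at the 0.05 level. A two-sided two-sample t-test (noncentral t) gives 82.1% with 4 per arm and 61.9% with 3 per arm, so the figure reproduces.

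**Simple Week 8 comparison.** SAP 7.2 lists "Mean change differences with 95% CI". In SD units with a pooled t interval, half-width = t(0.975, n1+n2−2) × √(1/n1 + 1/n2).

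| Phenserine : donepezil | SE | t | Half-width | Change | Power at 2.45 SD |
|---|---|---|---|---|---|
| 12 : 4 | √(1/12+1/4) = 0.577 | 2.145 | 1.24 | – | 97.6% |
| 12 : 3 | √(1/12+1/3) = 0.645 | 2.160 | 1.39 | +13% | 93.9% |
| 12 : 2 | √(1/12+1/2) = 0.764 | 2.179 | 1.66 | +34% | 83.7% |

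**Mixed model, one donepezil Week 8 value missing.** Assume compound symmetry with within-person correlation ρ between changes, and treat the covariance as known. The other three visits predict Week 8 with R² = 3ρ²/(1+2ρ). The donepezil Week 8 mean then has variance (1−R²)/3 + R²/4, and the phenserine mean has variance 1/12. The SE with all values present is 0.577.
- ρ = 0: R² = 0; SE = √(0.3333+0.0833) = 0.645, a rise of 11.8%.
- ρ = 0.5: R² = 0.375; SE = √(0.3021+0.0833) = 0.621, a rise of 7.5%.
- ρ = 0.9: R² = 0.868; SE = √(0.2610+0.0833) = 0.587, a rise of 1.6%.

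The SE of the treatment effect averaged over the four visits rises by only 0.1% (ρ = 0.9) to 3.1% (ρ = 0).

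**How often.** The documents give no off-window rate, so p is an assumption, with visits taken as independent. The chance of losing at least one of 4 donepezil Week 8 samples is 1 − (1−p)⁴:
- p = 5%: 1 − 0.95⁴ = 19%
- p = 10%: 1 − 0.90⁴ = 34%
- p = 20%: 1 − 0.80⁴ = 59%

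Of 16 × 4 = 64 post-baseline samples, these rates would remove about 3, 6 and 13.

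**The case against.** The strongest reply is that the window is pre-specified, the trial is exploratory, and SAP 2.4 still allows the values to be listed and summarised. The two sections can also be partly reconciled: a minor deviation keeps the participant in the analysis population, while 2.4 governs single values. That removes a flat contradiction. It still gives no reason for omitting a value whose timing the SAP regards as immaterial, and listing a value does not put it into the estimate.

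The reply is right to limit four stronger readings that a reader might infer.
- **One late visit costs a quarter of the comparator outright.** It costs a quarter at that visit, which is 1 of the arm's 16 post-baseline values. The whole person is lost only if complete-case in SAP 6 means participants with every visit. That fits poorly with the mixed model and with the one-sample entry rule for mITT in SAP 4.3.
- **A Day 20 early-termination sample will be analysed as Week 8 while a Day 60 sample is dropped.** SAP 3.3 says where applicable, and a Day 20 value also fails the Day 56 window in 2.4. Protocol 7 also asks for endpoint assessments both at drop-out and at Week 8. The conflict is unresolved, and this is only one way to resolve it.
- **The exclusions bias the treatment contrast.** Visits might slip for tolerability reasons that differ by arm, but the documents do not show this and no bias can be quantified from them.
- **The trial loses its power.** At the assumed 2.45 SD, power is 93.9% at 12:3, and the SAP disclaims formal testing.

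The reply is also right that reassigning every sample by calendar day would be a poor remedy. Phenserine steps up at Weeks 2 and 4, so a pre-escalation Week 2 sample taken on Day 21 could be relabelled Week 4.

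**Conclusion.** The point holds as a loss of precision with no stated justification. The exclusion, the minor-deviation label and the lack of any planned comparative analysis including these samples are all in the text. The +13% (one loss) and +34% (two losses) apply to the simple Week 8 mean difference. For one loss, the mixed model reduces the cost to about 2% to 12% on the Week 8 SE. SAP 7.2 itself warns that the model may not converge, and the results would then be descriptive.

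The sizes rest on a common SD, a compound-symmetric correlation between 0 and 0.9, and an assumed off-window rate. The change is worth making because it is cheap and the comparator is very small. The result is not shown to be biased or underpowered.

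**What to change.** Amend the SAP before database lock and biomarker unblinding.
- **SAP 2.4, scheduled visits.** Include all on-treatment exosome samples in the primary analysis under their nominal scheduled visit, so that each stays with its dose step, and record the actual sampling day. Define on-treatment from the recorded last dose. Reword the sentence on secondary analyses so that it does not reinstate the exclusion.
- **SAP 2.4, other samples.** Map early-termination and unscheduled samples to the nearest scheduled visit by actual day. If two samples compete for one visit, use the one closest to target.
- **SAP 3.3.** State that an early-termination sample is not automatically labelled Week 8.
- **Sensitivity analysis.** Repeat the primary analysis restricted to samples within 3 days of target.
- **SAP 3.4.2.** Keep off-window visits as minor deviations.
- **SAP 6.** Say whether complete-case refers to values or to participants.

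The cost is SAP wording and one additional run, with no new data. The downside is somewhat more spread in sampling day and time on dose within a visit, which the in-window sensitivity analysis checks.
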